### **5.1.3 Labeling**

All labels for the individual cartons will contain the protocol number, kit number, description of the content of the package, dosing instructions, an investigational drug warning, storage conditions, and the sponsor company name and address. It will also contain space to document subject number, site number, subject initial, and dosing period number or date dispensed.

The carton label will consist of 2 panels, with 1 detachable panel that will be removed and kept with the site's study records (e.g., affixed to the study medication dispensing log page or subject source records) at the time of dispensing. Space is provided on both panels of the card label to record subject number, dispensing date and assigned treatment period. All IP labels comply with all applicable federal and local regulations.

### **5.1.4 Storage of Clinical Supplies**

Clinical supplies must be stored in compliance with label requirements in a secure place and kept at room temperature; 20° - 25°C (68° -77°F) with excursions permitted to 15°C to 30°C (59°F- 86°F). The approved expiration date for ONZETRA Xsail is 36 months.

### **5.1.5 Study Medication Administration**

All subjects will receive AVP-825 or matching placebo according to the kit number assigned by an Interactive Web Response System (IWRS) randomization scheme. Designated staff at each site will dispense study medication and train subjects on the use of a drug device combination product using a demonstration kit clearly labelled as 'demo kit'. The subject will self-administer the study medication following instruction for use provided in the study medication kit.

## **5.2 Accountability of Study Supplies**

### *Receipt of Supplies*

---

The IP will be shipped by the sponsor directly to the study sites.

The investigator is responsible for maintaining an inventory of each shipment of IP received and comparing it with the accompanying Drug Accountability Report/Material Shipping Form. The investigator will verify the accuracy of the information on the form, sign and date it, and return the form to the sponsor or its representative. All IP supplied is for use only in this study and should not be used for any other purpose. All study drug material kit numbers will also be recorded and tracked at the site using the Drug Accountability Log.

Record of Dispensing

Accurate records of all kits dispensed for individual subjects will be made in the appropriate section of the subject's drug accountability records. This document will contain the following information: (i) the subject number to whom the drug was dispensed; (ii) the date(s) and quantity of the drug dispensed to the subject; and (iii) the kit number assigned to the subject via IRT system.

Additionally, the detachable panel of the 2-panel label from each kit will be removed and kept with the site's study records (e.g., affixed to a study medication subject drug dispensing logpage) at the time of dispensing. Space is provided on both panels of the kit label to record subject number, site number, subject initial, and dosing period number or date dispensed.

Unused Supplies

At the end of the study, all unused investigational supplies must be inventoried on the Drug Accountability Log and returned to the sponsor or its representative, along with a completed and signed Drug Accountability Report/Material Shipping Form. If any study medication is lost or damaged, it should be indicated on the form.

### **5.3 Subject Compliance**

At screening/enrollment (Visit1) and randomization (Visit 2), subjects will be trained on the use of the study medication and completion of the diary. Subjects will be instructed to treat their migraine headache as soon as it reaches an intensity of moderate to severe, and record information in the diary for each attack during the treatment phases. Subjects will be instructed to bring their diary and used study medication to the site at Visits 2 and 3 for review and compliance check.

### **5.4 Concomitant and Prohibited Medication**

All medications and other treatments taken by the subjects during the study, including those treatments initiated 30 days prior to the start of the study, must be recorded on the electronic

---

Case Report Form (eCRF).

During the study, subjects will be permitted to continue to take migraine prophylactic medications they were taking at screening/enrollment provided they had been on a constant regimen for at least 7 days prior to screening/enrollment. The regimen is to remain constant throughout the study, except for necessary changes for medical or safety reasons. If a prophylactic regimen changes after screening/enrollment, then the subject is to postpone treatment of a migraine with investigational product until the new prophylactic regimen has been in place for at least 7 days.

The following medications, OTC or prescription, are prohibited during the specified timeframe:

- Any acute medications for migraine, including short acting NSAID-containing compound, other simple analgesics, as well as anti-emetic medications are prohibited for the following duration: 6 hours before dosing to 2 hours after treatment with investigational product.
- Analgesics containing morphine, codeine, a barbiturate or an opioid derivative 24 hours before and 24 hours after taking investigational product.
- Ergotamine containing drugs, ergotamine derivatives or any 5-hydroxytryptamine 1 (5-HT1) agonist (including but not limited to sumatriptan, naratriptan, zolmitriptan, almotriptan, frovatriptan, eletriptan or rizatriptan) are also excluded within 24 hours before, and 24 hours after treatment with investigational product.
- Monoamine oxidase-A (MAO-A) inhibitors are excluded for at least 4 weeks before screening/enrollment or at any time during the course of this study.
- In addition, use of any investigational drug within 4 weeks prior to randomization or during the study is prohibited.

## 5.5           Rescue Medication

Subjects are allowed to take rescue medication 2 hours after taking the study treatment and after completing the 2-hour post-dose diary questions. The use of rescue medication will be recorded on the diary. Rescue medication may include the following:

- OTC pain reliever – OTC monotherapy pain reliever such as acetaminophen or nonsteroidal anti-inflammatory drugs (NSAIDs), not exceeding the maximum recommended dose
- Prescription NSAIDs – prescription NSAID monotherapy should be prescribed by the

---

investigator specifically for the subject for the acute treatment of migraine, and should be used according to the package insert

- OTC anti-emetics – OTC anti-emetics commonly used to treat nausea symptoms during migraine attacks, not exceeding the maximum recommended dose
- Prescription anti-emetics – prescription anti-emetics should be prescribed by the investigator specifically for the subject for the symptoms of migraine, and should be used according to the package insert

For any questions regarding rescue medication, the Medical Monitor (MM) should be consulted. Rescue medications will not be supplied by the sponsor.

**6****STUDY ASSESSMENTS AND PROCEDURES****6.1 Efficacy Measures****6.1.1 Primary Measure**

Subjects will record in the diary if they are headache pain free for each migraine attack (1 and 2), at the following timepoints post dose: 15, 30, 60, 120 mins, 3, 4, and 24 hours.

The primary endpoint is headache pain-free at 120 minutes following treatment of Migraine Attack 2.

**6.1.2 Secondary Measures**

Subjects will record the following in the diary for each migraine attack (1 and 2) at the timepoints specified in Table 2:

- Headache severity score (scale of 0 to 3, where 0 = none, 1 = mild, 2 = moderate, 3 = severe)
- Nausea, vomiting photophobia, phonophobia (yes/no for each symptom)
- Ability to function (response to 'how do you rate your ability to do school-work or perform your usual activities?' on a 5-point scale [normal, mildly impaired, moderately impaired, severely impaired, I require bedrest])
- Time of recurrence of headache, defined as an increase from a headache severity score of 0 (none) or 1 (mild) pain to 2 (moderate) or 3 (severe)
- Use and time of rescue medication
- Bilateral headache (yes/no)
- Intensity increased by movement (yes/no)

**6.2 Safety****6.2.1 Adverse Events****6.2.1.1 Definitions**

An adverse event (AE) is any untoward medical occurrence or unintended change (including physical, psychological, or behavioral) from the time ICF is signed, including inter-current

illness, which occurs during the course of a clinical trial after treatment has started, whether considered related to treatment or not. An AE can therefore be any unfavorable and unintended sign (including an abnormal laboratory finding, for example), symptom, or disease temporally associated with the use of a medicinal product, whether or not considered related to the medicinal product. Changes associated with normal growth and development that do not vary in frequency or magnitude from that ordinarily anticipated clinically are not AEs (e.g., onset of menstruation occurring at a physiologically appropriate time).

Clinical AEs should be described by diagnosis and not by symptoms when possible (e.g., cold, seasonal allergies, instead of “runny nose”).

Migraine headache and associated symptoms (i.e., photophobia, phonophobia, nausea, vomiting) will not be captured as AEs unless the investigator feels they differ in frequency, intensity or duration from the subject’s baseline condition.

An overdose is a deliberate or inadvertent administration of a treatment at a dose higher than specified in the protocol and higher than known therapeutic doses. It must be reported irrespective of outcome even if toxic effects were not observed.

AEs will be graded on a 3-point scale and reported in detail as indicated on the eCRF:

Mild: easily tolerated, causing minimal discomfort and not interfering with normal everyday activities

Moderate: sufficiently discomforting to interfere with normal everyday activities

Severe: incapacitating and/or preventing normal everyday activities

The relationship of each AE to study medication should be determined by the investigator using the following explanations:

Not related: the event is clearly related to other factors such as the subject’s clinical state, therapeutic interventions, or concomitant medications administered to the subject

Unlikely related: the event is most likely produced by other factors such as the subject’s clinical state, therapeutic interventions, or concomitant medications administered to the subject; and does not follow a known response pattern to the study medication

Possibly related: the event follows a reasonable temporal sequence from the time of drug administration; and/or follows a known response pattern to the study medication; but could have been produced by other factors such as the subject’s clinical state, therapeutic interventions, or concomitant medications

---

administered to the subject

Related: the event follows a reasonable temporal sequence from the time of drug administration; and follows a known response pattern to the study medication; and cannot be reasonably explained by other factors such as the subject's clinical state, therapeutic interventions, or concomitant medications administered to the subject

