**Table 2 Time and Event Schedule for Migraine Attacks 1 and 2**

	Pre-Dose	Dosing	15 min	30 min	60 min	120 min	3 Hours	4 Hours	24 Hours
Record efficacy assessments in diary:									
Pain free (Yes/No)			X	X	X	X	X	X	X
Headache severity score	X		X 						
Migraine symptoms (separate questions): Nausea, vomiting, photophobia, phonophobia	X		X	X	X	X			X
Dose of study drug medication		X							
Bilateral headache (Yes/No)	X		X 		X 				
Intensity increased by movement (Yes/No)	X		X 		X 				
Ability to function question	X		X	X	X	X			X
Time of recurrence of headache						X 			X 
Rescue medication						X 			X 

Min = minutes;

1 Assessed only if response to pain free question is "No"

2 Assessment should be made after 120 minutes.

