### 8.2 Efficacy Analysis

The primary efficacy endpoint of the study is headache pain-free at 120 minutes following treatment of Migraine Attack 2. Treatment comparison will be performed by using the Cochran-Mantel-Haenszel (CMH) test stratified by age group (12-14 years or 15-17 years) and baseline migraine pain severity (moderate or severe). Secondary and exploratory efficacy endpoints will be analyzed similarly, or appropriate statistical tests will be used. Efficacy assessments after taking rescue medication will be set to missing. Missing data will be imputed by treatment failure, i.e., headache pain-free = no. *Secondary efficacy endpoints (Migraine Attack 2):*

- Headache relief (defined as a reduction in pain intensity from moderate or severe [grade 2 or 3] at baseline to none or mild [grade 0 or 1] at 120 minutes)
- Headache pain-free by time (other than at 120 minutes)
- Headache relief by time (other than at 120 minutes)
- Change from baseline in headache severity by time
- Sustained pain relief, defined as headache relief [headache severity mild (grade 1) or none (grade 0)] at 2 hours with no worsening of headache, use of a second dose of study medication, or rescue medication taken through 24 hours after dose
- Sustained pain freedom, defined as pain freedom [headache severity none (grade 0)] at 2 hours with no recurrence of headache, use of a second dose of study medication or rescue medication taken through 24 hours after dose
- Rescue medication use and time to rescue medication
- Number of subjects with nausea, phonophobia, photophobia, or vomiting by time
- Number of subjects who return to ‘normal’ functioning by time

---

- Time to recurrence of headache defined as an increase from a headache severity score of 0 (none) or 1 (mild) at 2 hours to 2 (moderate) or 3 (severe) within 24 hours

*Exploratory efficacy endpoints (Migraine Attack 2):*

- Sustained pain relief (1 to 2 hours), defined as headache relief [Headache severity mild (grade 1) or none (grade 0)] at 60 minutes with no worsening of headache, use of a second dose of study medication, or rescue medication taken through 120 minutes after dose
- Sustained pain freedom (1 to 2 hours), defined as pain freedom [Headache severity none (grade 0)] at 60 minutes with no recurrence of headache, use of a second dose of study medication or rescue medication taken through 120 minutes after dose
- Bilateral headache at predefined timepoints

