## **8.3 Safety Analysis**

Safety will be assessed by the following measurements: AEs, physical examination, vital signs, and urine pregnancy test. All safety measures will be summarized by treatment.

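### New nausea after dosing can be missed by the adverse event rule and offset by relief in the planned symptom counts; a by-arm new-onset table from the existing diary data would show it

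*Combined protocol and SAP*

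**What the plan says.** Section 6.2.1.1 first defines an adverse event broadly, covering any unfavourable "symptom, or disease temporally associated with the use of a medicinal product, whether or not considered related to the medicinal product". It then makes an exception: "Migraine headache and associated symptoms (i.e., photophobia, phonophobia, nausea, vomiting) will not be captured as AEs unless the investigator feels they differ in frequency". Intensity and duration are further grounds for recording, and the reference in each case is the subject's baseline condition. The protocol does not say whether that condition is the subject's usual attack or the state just before the treated dose.

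The diary collects these symptoms directly. Table 2 lists "Migraine symptoms (separate questions): Nausea, vomiting, photophobia, phonophobia" before dosing, at 15, 30, 60 and 120 minutes, and at 24 hours. Section 6.1.2 gives the format: "Nausea, vomiting photophobia, phonophobia (yes/no for each symptom". No intensity is recorded.

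Their only listed analysis is a secondary efficacy endpoint in the synopsis and section 8.2: "Number of subjects with nausea, phonophobia, photophobia, or vomiting by time". No split by pre-dose status is given. Section 8.3 does not list the diary symptoms among the safety measures: "Safety will be assessed by the following measurements: AEs, physical examination, vital signs, and urine pregnancy test". It adds: "All safety measures will be summarized by treatment".

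**The concern.** The study objective (section 2) is safety as well as efficacy against placebo, and section 1 describes gastrointestinal symptoms as prominent in this age group. The adverse event exception may therefore apply to many subjects.

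There are two routes by which an excess of new nausea on the active arm could reach the report, and each can fail. The adverse event table depends on a judgement against an undefined reference. If the reference is the usual attack, new nausea in someone who usually has nausea need not differ from it. The efficacy count is complete, but it is net: a subject whose nausea persists and a subject whose nausea began after dosing are counted alike. If the drug relieves existing nausea in some subjects and causes it in others, the two effects cancel in that count. Both sets of tables could then look favourable while the diary held evidence of an excess.

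**Working it through.** **Arm size.** Section 8.4 gives 118 per arm for 30% versus 15%, two-sided alpha 0.05 and about 80% power. The unpooled formula reproduces it: (1.960 + 0.842)² × (0.30×0.70 + 0.15×0.85) / 0.15² = 117.7, so 118. Power at 118 per arm is 79.2%. The figure is not in dispute and serves only as the arm size below.

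**Formula.** Let b be the proportion with the symptom pre-dose, r the proportion of those in whom it has resolved, and e the proportion of initially symptom-free subjects who have it at the timepoint. The planned count estimates

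net = b(1 − r) + (1 − b)e.

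All values of b, r and e below are assumptions; the documents give none.

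**Illustration at 120 minutes.** Take r = 60% versus 40% and e = 10% versus 3% (AVP-825 versus placebo).

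| Pre-dose b | Net, AVP-825 | Net, placebo | Difference in favour of drug |
|---|---|---|---|
| 40% | 0.4×0.4 + 0.6×0.10 = 22.0% | 0.4×0.6 + 0.6×0.03 = 25.8% | 3.8 points |
| 50% | 0.5×0.4 + 0.5×0.10 = 25.0% | 0.5×0.6 + 0.5×0.03 = 31.5% | 6.5 points |
| 60% | 0.6×0.4 + 0.4×0.10 = 28.0% | 0.6×0.6 + 0.4×0.03 = 37.2% | 9.2 points |

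At b = 50%, 59 subjects per arm are symptom-free pre-dose. New onset is 59 × 0.10 = 5.9 versus 59 × 0.03 = 1.8, a ratio of 3.3.

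**Exact cancellation.** With b = 50%, r = 50% versus 40% and e = 15% versus 5%, net is 0.25 + 0.075 = 32.5% on AVP-825 and 0.30 + 0.025 = 32.5% on placebo, about 38 of 118 in each arm. New onset is about 9 versus 3 of 59.

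**How much relief is needed to hide an excess.** Net counts are equal when b × (extra resolution) = (1 − b) × (extra new onset). A 10-point excess of new onset is offset by extra resolution of:

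- 23 points at b = 30%
- 15 points at b = 40%
- 10 points at b = 50%
- 6.7 points at b = 60%

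**Earlier timepoints.** Keep b = 50% and e = 10% versus 3%. With no resolution yet, net is 0.50 + 0.05 = 55.0% versus 0.50 + 0.015 = 51.5%, an excess on the active arm. With resolution of 10% versus 5%, it is 0.45 + 0.05 = 50.0% versus 0.475 + 0.015 = 49.0%. Masking therefore depends on timing: an early count could show an excess that the 120-minute count does not.

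**Vomiting.** A 7-point excess of new onset needs extra resolution of 0.90 × 7 / 0.10 = 63 points if 10% vomit pre-dose. At 5% it needs 0.95 × 7 / 0.05 = 133 points, which is impossible. If vomiting is uncommon before dosing, the planned count already largely shows new vomiting.

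**The case against.** A reader might infer that post-dose nausea is barred from the adverse event data, or that an excess would appear in no planned table. The documents support neither.

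- The exception is conditional, and an investigator may record a symptom judged to differ. If the baseline term means the pre-dose state of the treated attack, nausea that was absent before dosing and present after it could qualify. Section 6.2.1.2 itself uses nausea as its example of a severe but non-serious event.
- The investigator need not rely on recall at the exit visit, about 10 days after Attack 2. Section 9.3 has staff review the e-diary responses at Visits 2 and 3.
- The endpoint is reported at each timepoint, so an excess must be offset at all of them to stay hidden throughout.
- Every symptom rate above is assumed, and section 1 describes few triptan-related adverse effects in adults. New nausea can also be the untreated attack progressing.
- The added table would be descriptive. Rounding the illustration to 6 of 59 versus 2 of 59 gives a two-sided Fisher p of 0.27.
- The documents contain no table shells, so a missing table could be called lack of detail.

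These points limit the claim to what can happen, and mainly to nausea. They do not remove it. Diary review gives the investigator the data but not the definition to apply, so recording may vary between sites. Progression of the attack occurs in both arms, so a comparison by arm accounts for it. The gap is more than missing detail, because following the stated rule and the stated count exactly still leaves new onset unseparated from relief.

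**Conclusion.** The concern holds as a possibility. New nausea after dosing can go unrecorded as an adverse event if the baseline term is read as the usual attack pattern. The net count can obscure an excess at some or all timepoints. Under the assumed rates, a roughly threefold excess in new onset coexists with a 120-minute count that is level or favours the drug by 3.8 to 9.2 points as pre-dose prevalence runs from 40% to 60%. Those sizes rest wholly on the assumed rates.

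A reader might go further and conclude that the drug causes an excess of nausea or that the plan will hide one. The documents give no symptom rates and no evidence of an excess, so that does not follow. The randomized comparison of net symptoms remains valid, and the primary endpoint, power and error rate are untouched. The change is a worthwhile, inexpensive improvement to safety reporting.

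**What to change.** The wording of the adverse event exception can stay. Two additions are needed.

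1. **In section 8.3, add a descriptive table by arm for Migraine Attack 2.** Use safety population subjects who treated that attack, grouped by treatment received. Give the number and percentage with nausea, and separately with vomiting, absent pre-dose and present at any of 15, 30, 60 or 120 minutes. The denominator is subjects with the symptom recorded as absent pre-dose. That status is fixed before dosing and under blinding, so the arms remain comparable.
   - Use recorded diary answers only. Section 8.2 says "Efficacy assessments after taking rescue medication will be set to missing" and then imputes missing data as failure, which would create false events here.
   - Leave out the 24-hour entry, because section 5.5 allows rescue from 2 hours. The period to 120 minutes is largely free of it: section 5.4 excludes acute medication and anti-emetics until then.
   - Refer to this table wherever adverse event rates for nausea or vomiting are reported.
2. **In section 6.2.1.1, state which meaning of baseline condition applies:** the usual attack pattern or the pre-dose state of the treated attack.

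The cost is one extra table from data already collected and one sentence of definition. The safety profile may look slightly less favourable. Sample size, power and the primary analysis do not change.

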### **6.2.1.2      Serious Adverse Events**

A Serious Adverse Event (SAE) is any AE occurring at any dose that results in any of the following outcomes:

1. Death
2. Life-threatening experience (one that places the subject, in the view of the initial reporter, at immediate risk of death from the AE as it occurred, i.e., it does not include an AE that, had it occurred in a more severe form, might have caused death)
3. Persistent or significant disability/incapacity (disability is a substantial disruption of a person's ability to conduct normal life functions)
4. In-patient hospitalization or prolongation of hospitalization
5. Congenital anomaly/birth defect

Important medical events that may not result in death, or be life-threatening, or require hospitalization may be considered an SAE when, based upon appropriate medical judgment, they may jeopardize the subject or require medical or surgical intervention to prevent one of the outcomes listed in the definition.

The terms "cancer" and "overdose" are not considered to be SAEs, but if a subject experiences cancer or overdose, they are still reportable as AEs.

Pregnancy is not considered to be an AE or an SAE, unless a complication occurs that meets the requirements for an AE or SAE but must be reported on a pregnancy report form. Women who are pregnant or likely to become pregnant are excluded from this study. In the event a subject becomes pregnant during the study, study medication must be discontinued, a pregnancy report form must be completed to capture potential drug exposure during pregnancy, and the pregnancy must be reported within 24 hours of notice. Any pregnant subject must be followed until the outcome of her pregnancy is known (i.e., normal delivery, abnormal delivery, spontaneous/voluntary/therapeutic abortion). The pregnancy (i.e., the mother and the fetus) must be followed up through delivery with regard to outcome.

---

A pregnancy report form must also be completed in the event that a female partner of a male subject becomes pregnant within 30 days after his last dose of study medication.

The term ‘severe’ is a measure of intensity; thus, a severe AE is not necessarily serious. For example, nausea of several hours’ duration may be rated as severe but may not be clinically serious.

